8.2 Lactation

Risk Summary

Based on two small clinical studies, methadone was present in low levels in human milk, but the exposed infants in these studies did not show adverse reactions. Based on an average milk consumption of 150 mL/kg/day, an infant would consume approximately 17.4 mcg/kg/day which is approximately 2% to 3% of the oral maternal dose. There have been rare case reports of sedation and respiratory depression in infants exposed to methadone through breast milk (see Data). Monitor infants exposed to methadone hydrochloride tablets through breast milk for excess sedation and respiratory

#UTHealth Houston

depression. The developmental and health benefits of breastfeeding should be considered along with the mother's clinical need for methadone and any potential adverse effects on the breastfed child from the drug or from the underlying maternal condition.

Data

In a study of ten breastfeeding women maintained on oral methadone doses of 10 to 80 mg/day, methadone concentrations from 50 to 570 mcg/L in milk were reported, which, in the majority of samples, were lower than maternal serum drug concentrations at steady state. Peak methadone levels in milk occur approximately 4 to 5 hours after an oral dose.

In a study of twelve breastfeeding women maintained on oral methadone doses of 20 to 80 mg/day, methadone concentrations from 39 to 232 mcg/L in milk were reported. Based on an average milk consumption of 150 mL/kg/day, an infant would consume approximately 17.4 mcg/kg/day, which is approximately 2% to 3% of the oral maternal dose. Methadone has been detected in very low plasma concentrations in some infants whose mothers were taking methadone.

8.3 Females and Males of Reproductive Potential

Infertility

The effect of methadone hydrochloride tablets on fertility is unknown. Chronic use of opioids may cause reduced fertility in females and males of reproductive potential. It is not known whether these effects on fertility are reversible [see Adverse Reactions (6), Clinical Pharmacology (12.2), Nonclinical Pharmacology (13.1)]. Reproductive function in human males may be decreased by methadone treatment. Reductions in ejaculate volume and seminal vesicle and prostate secretions have been reported in methadone-treated individuals. In addition, reductions in serum testosterone levels and sperm motility, and abnormalities in sperm morphology have been reported.

In published animal studies, methadone produces a significant regression of sex accessory organs and testes of male mice and rats and administration of methadone to pregnant rats reduced fetal blood testosterone and androstenedione in male offspring [see Nonclinical Toxicology (13)].

8.4 Pediatric Use

The safety, effectiveness, and pharmacokinetics of methadone in pediatric patients below the age of 18 years have not been established.

8.5 Geriatric Use

Clinical studies of methadone did not include sufficient numbers of subjects aged 65 and over to determine whether they respond differently compared to younger subjects. Other reported clinical experience has not identified differences in responses between elderly and younger patients.

Elderly patients (aged 65 years or older) may have increased sensitivity to methadone. In general, use caution when selecting a dosage for an elderly patient, usually starting at the low end of the dosing range, reflecting the greater frequency of decreased hepatic, renal, or cardiac function and of concomitant disease or other drug therapy.

Respiratory depression is the chief risk for elderly patients treated with opioids, and has occurred after large initial doses were administered to patients who were not opioid-tolerant or when opioids were co-administered with other agents that depress respiration. Titrate the dosage of methadone hydrochloride tablets slowly in geriatric patients and monitor closely for signs of central nervous system and respiratory depression [see Warnings and Precautions (5.8)].

Methadone is known to be substantially excreted by the kidney, and the risk of adverse reactions to this drug may be greater in patients with impaired renal function. Because elderly patients are more likely to have decreased renal function, care should be taken in dose selection, and it may be useful to monitor renal function.

#UTHealth Houston

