Patients will be randomized to either Oral Methadone tablets the interventional group or Control group that will receive usual care with IV Fentanyl or hydromorphone per hospital protocols. Patients on the methadone group will be started on Methadone 5mg, 10mg or 15mg every 8 hours via a feeding tube depending on Fentanyl drip rate (0-100mcg/hr, 100-200mcg/hr or >200mcg/hr) or hydromorphone drip rate (0-1.5mg/hr, 1.5-3mg/hr, or >3mg/hr), Appendix3. The rate of Fentanyl or hydromorphone will be reduced by 25% initially to bring patient to a desired RASS (Richmond Agitation Sedation Scale score) as requested by the physician. While the control group will Not get any medication and will be weaned off opioids as per usual care.

c. Rationale for Study Population

In order to test our hypothesis our population of target needed to be patients admitted to the ICU who have been on mechanical ventilation for more the 72 hours on sedation with opioids. This gives us the opportunity to be able to compare outcomes between those that will receive methadone to those that will not

d. Rationale for Study Design

A randomized control trial gives us the best tool devoid of selection bias as well as controlling for potential confounders.

#UTHealth Houston

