5. STUDY DESIGN

5.1. Summary of Study Design

The study is randomized clinical trial. The duration of the study is 2 years. Patients will be screened to confirm they meet study criteria. Consent will be obtained from the legal authorized representative. Initial demographic data will be obtained using REDCap Database. Patients will be randomized to either Oral Methadone tablets or Non-Methadone group. The control group will receive usual care with IV Fentanyl or hydromorphone per hospital protocols as on appendix 1. Patients on the methadone group will be started on Methadone 5mg, 10mg or 15mg every 8 hours depending on Fentanyl drip rate (0-100mcg/hr, 100-200mcg/hr or >200mcg/hr) or hydromorphone drip rate (0-1.5mg/hr, 1.5-3mg/hr, or >3mg/hr). The rate of Fentanyl or hydromorphone will be reduced by 25% initially. If patients require additional sedation later, this will be administered per usual care and the total amount of additional opioids will be documented and used for analysis as morphine milligram equivalents (MME). Likewise, patients could be weaned more than 25% if they showed signs of tolerance to lesser sedation.

At Subsequent encounters: Rate of Fentanyl or Hydromorphone drip will be reduced by 25% every 24 hours until the patient is extubated from the ventilator.

Continuous IV opioids for analgesia for patients on mechanical ventilation is routine clinical care and will not be denied to patients. Once patients are extubated oral methadone will be discontinued and patient monitored for any opioid withdrawal symptoms and treated per protocol as shown on appendix 2 based on their clinical opiate withdrawal scale (COWS) appendix 4. For those with a score of less than 25 oral methadone will no longer be required. For those with a COWS score of >25 methadone will be resumed for a short taper of 3 days. The above can be illustrated as on study protocol flow on Appendix 5 and details on methadone taper as on Appendix 2.

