7. TREATMENT

7.1. Rationale for Selection of Dose

Dose selection will be based on currently approved protocol which is attached as an appendix 2.

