8.6 Hepatic Impairment

Methadone pharmacokinetics have not been extensively evaluated in patients with hepatic insufficiency. Methadone is metabolized by hepatic pathways; therefore, patients with liver impairment may be at risk of increased systemic exposure to methadone after multiple dosing. Start these patients on lower doses and titrate slowly while carefully monitoring for signs of respiratory and central nervous system depression.

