8.7 Renal Impairment

Methadone pharmacokinetics have not been extensively evaluated in patients with renal insufficiency. Since unmetabolized methadone and its metabolites are excreted in urine to a variable degree, start these patients on lower doses and with longer dosing intervals and titrate slowly while carefully monitoring for signs of respiratory and central nervous system depression.

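### For methadone-arm patients with renal impairment, or hepatic impairment short of the exclusion, the dose rule, the cited package insert and Section 7.3 give three incompatible instructions

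*Combined protocol and SAP*

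**What the plan says.** **Dose rule.** Under Section 1.2 b (Rationale for Doses Selected), methadone-arm patients are "started on Methadone 5mg, 10mg or 15mg every 8 hours via a feeding tube depending on Fentanyl drip rate", or on the hydromorphone rate. Section 5.1 repeats the rule: "started on Methadone 5mg, 10mg or 15mg every 8 hours depending on Fentanyl drip rate". Neither place has a term for age, kidney function or liver function, and the interval is the same for everyone.

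**Source of the rule.** Section 1.2 b points to the package insert at the end of the tiers: "or >3mg/hr), Appendix3". Section 7.1 points elsewhere: "Dose selection will be based on currently approved protocol which is attached as an appendix 2".

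**Package insert (Appendix 3).**
- Renal impairment (8.7): "start these patients on lower doses and with longer dosing intervals and titrate slowly".
- Hepatic impairment (8.6): "Start these patients on lower doses and titrate slowly". No change of interval is mentioned.
- Age 65 or older (8.5), introduced as a general statement: "use caution when selecting a dosage for an elderly patient, usually starting at the low end of the dosing range".

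**Warnings and restrictions.** Section 7.3 lists renal impairment, hepatic impairment and debilitated patients among those in whom the drug is warned against. Section 7.4, for specific restrictions or requirements, is entered as not applicable.

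**Eligibility.** Section 3.3 sets a lower age limit of 18 and no upper limit. Section 3.4 excludes end-stage liver disease, defined by an INR of 2 or more without warfarin and/or bilirubin at 1.5 times normal. None of its 14 items concerns the kidney.

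**Data.** Appendix 6 records age, APACHE II and total SOFA. It has no field for creatinine or renal replacement therapy.

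**The concern.** A patient with renal impairment can be randomised to methadone without breaking any eligibility criterion. What that patient should then receive depends on which page the treating team opens. One page gives the standard tier every 8 hours, another a lower dose at a longer interval, and a third advises against the drug. Hepatic impairment milder than the Section 3.4 definition raises the same problem, apart from the interval. For patients aged 65 or older the conflict is softer: the insert advises caution and the dose rule does not respond to it.

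Two things are at stake. The first is safety. Dosing exactly as Sections 1.2 b and 5.1 say would treat a renally impaired patient against both Section 7.3 and the insert cited for the rule. The second is uniformity. Two hospitals recruit, with separate randomisation tables, and each could settle the conflict differently, so the intervention would not be one defined regimen. Only the methadone arm is exposed to this, because only that arm receives the drug. If an excess of sedation, respiratory or QTc events appeared, the form would not let the trial team read them against renal function.

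**Working it through.** **1. The instructions side by side.** The plan states no numerical result on this point, so the main check compares texts.

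| Methadone-arm patient | Sections 1.2 b and 5.1 | Appendix 3 | Section 7.3 | Section 3.4 |
|---|---|---|---|---|
| Renal impairment | Tier by infusion rate, every 8 h | Lower start, longer interval (8.7) | Warned against | No criterion |
| Hepatic impairment, not end-stage | Tier by infusion rate, every 8 h | Lower start (8.6) | Warned against | Not excluded |
| Age 65 or older, no organ impairment | Tier by infusion rate, every 8 h | General caution, usually the low end (8.5) | Age not named | No upper limit in 3.3 |

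In the first two rows the three instructions cannot all be followed. In the third row one caution is unaddressed, which is weaker than a contradiction.

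**2. What the tiers give.** Three doses a day: 3 × 5 = 15, 3 × 10 = 30 and 3 × 15 = 45 mg/day. The dose rule does not vary these with age or organ function.

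**3. How much a fixed 8-hour interval could matter.** Inputs:
- interval 8 h (Sections 1.2 b and 5.1);
- half-life 8 to 59 h (Appendix 3, 2.4 and 12.3), with 24 h added as an assumed middle value;
- primary outcome at day 5 from intubation (Section 2.5), that is 120 h;
- entry after more than 72 h of ventilation (Section 3.3).

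Time available before day 5 is at most 120 − 72 = 48 h, or 48/8 = 6 doses.

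Under a one-compartment model (my assumption), the level relative to a single dose is:
- after six doses, (1 − 2^(−48/t)) / (1 − 2^(−8/t));
- at steady state, 1 / (1 − 2^(−8/t)).

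| Half-life t | After 6 doses | Steady state |
|---|---|---|
| 8 h | 0.984/0.500 = 2.0 | 2.0 |
| 24 h | 0.750/0.206 = 3.6 | 4.85 |
| 59 h | 0.431/0.0897 = 4.8 | 11.15 |

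Time to 90% of steady state is 3.32 × t: about 27 h at a half-life of 8 h and about 196 h at 59 h. The larger multiples therefore arise only in patients still ventilated and dosed well after day 5. That can happen: Section 5.1 stops methadone at extubation, and Section 4.2 allows up to 30 days of participation.

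**4. Sample size.** The planned 76 patients, 80 with dropout, rest on 50% v 20% extubated by day 5. Nothing in this point changes those figures.

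**The case against.** The strongest reply is that Section 7.3 already covers most of these patients. It warns against methadone in renal and hepatic impairment and in debilitated patients, and Section 3.4 removes the worst liver disease. A reader might infer that slow-clearing patients are simply enrolled and given the full schedule. The documents do not say that; they do not say what such a patient receives. This part of the reply stands. It does not remove the conflict, because the warning appears in neither the exclusions nor the dose rule, and Section 7.4 declares no restriction. Read literally, the entry for debilitated patients could cover much of a population ventilated for over 72 hours, so it does not work as a rule.

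Further points for the other side:
- **Dose source.** Section 7.1 names Appendix 2, which asks that its content be adapted to the individual patient by clinical judgement and advises caution in hepatic impairment. Section 6.3 has the drug dispensed on an ordinary physician order. Clinical latitude therefore exists. But Appendix 2 contains no renal or hepatic methadone dose step, and two different cited sources are a further inconsistency.
- **Age.** A reader might take Appendix 3 to require lower doses from 65. It gives only a general caution, sets no reduction, and adds that other clinical experience has shown no age difference in response.
- **Accumulation.** A reader might apply the 11-fold figure to the primary outcome. It is a steady-state value and cannot be reached in six doses. Nor is the half-life range specific to impaired patients.
- **Overall size of the tiers.** A reader might test them against Table 1 of Appendix 3. That table is restricted to conversion from oral opioids, so it settles nothing for intravenous infusions.
- **Data.** A reader might conclude that nothing is recorded to detect the problem. Age is on the form and Section 4.2 collects comorbidities. Only a separate measure of renal function is missing.

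**Conclusion.** The point holds as a contradiction in the stated rules, mainly one of patient safety. For renal impairment, and for hepatic impairment short of the Section 3.4 exclusion, the documents prescribe a standard tier every 8 hours, advise a reduced start (with a longer interval in renal impairment), and warn against use. For age 65 or older they leave a general caution unanswered.

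The size is only illustrative: about 2.0- to 4.8-fold accumulation within the six doses that fit before day 5, and 2.0- to 11-fold at steady state. This assumes one-compartment kinetics and the label's general half-life range. The share of patients affected is not given.

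Sedation from accumulation could delay extubation in the methadone arm, so an effect on the primary outcome is possible. A reader might go further and infer that the treatment effect would be diluted or reversed; nothing in the documents shows that. The matter should be settled before enrolment, because a patient dosed exactly as written could be treated against the protocol's own warning and the cited label.

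**What to change.** Before enrolment, reconcile Sections 1.2 b, 3.4, 5.1, 7.1, 7.3 and 7.4 with Appendix 3, 8.5 to 8.7, so that eligibility, the warnings and the dose rule agree:
- State whether renal impairment and hepatic impairment bear on eligibility, on the starting tier or on the interval.
- State whether age 65 or older has any bearing on the tier.
- Name one source for the dose rule.

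The clinical content is for the investigators to decide. What matters for the trial is that both hospitals apply one written rule.

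Add to Appendix 6 routinely measured creatinine and renal replacement therapy, at baseline and while on methadone, so that adverse events can be read against renal function.

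Reporting events to the DSMB by age and renal function is optional. With about 40 methadone patients the subgroups would be small.

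The cost is a wording amendment and two fields abstracted from the chart, with no extra tests and no extra patients.

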8.6 Hepatic Impairment

Methadone pharmacokinetics have not been extensively evaluated in patients with hepatic insufficiency. Methadone is metabolized by hepatic pathways; therefore, patients with liver impairment may be at risk of increased systemic exposure to methadone after multiple dosing. Start these patients on lower doses and titrate slowly while carefully monitoring for signs of respiratory and central nervous system depression.

8.7 Renal Impairment

Methadone pharmacokinetics have not been extensively evaluated in patients with renal insufficiency. Since unmetabolized methadone and its metabolites are excreted in urine to a variable degree, start these patients on lower doses and with longer dosing intervals and titrate slowly while carefully monitoring for signs of respiratory and central nervous system depression.

9 DRUG ABUSE AND DEPENDENCE

9.1 Controlled Substance

Methadone hydrochloride tablets contain methadone, a Schedule II controlled substance.

9.2 Abuse

Methadone hydrochloride tablets contain methadone, a substance with a high potential for abuse similar to other opioids including fentanyl, hydrocodone, hydromorphone, morphine, oxycodone, oxymorphone, and tapentadol. Methadone hydrochloride tablets can be abused and are subject to misuse, addiction, and criminal diversion [see Warnings and Precautions (5.1)].

All patients treated with opioids for pain management require careful monitoring for signs of abuse and addiction, since use of opioid analgesic products carries the risk of addiction even under appropriate medical use.

Prescription drug abuse is the intentional non-therapeutic use of a prescription drug, even once, for its rewarding psychological or physiological effects.

Drug addiction is a cluster of behavioral, cognitive, and physiological phenomena that develop after repeated substance use and includes: a strong desire to take the drug, difficulties in controlling its use, persisting in its use despite harmful consequences, a higher priority given to drug use than to other activities and obligations, increased tolerance, and sometimes a physical withdrawal.

"Drug-seeking" behavior is very common in persons with substance use disorders. Drug-seeking tactics include emergency calls or visits near the end of office hours, refusal to undergo appropriate examination, testing, or referral, repeated "loss" of prescriptions, tampering with prescriptions, and reluctance to provide prior medical records or contact information for other treating healthcare provider(s). "Doctor shopping" (visiting multiple prescribers to obtain additional prescriptions) is common among drug abusers and people suffering from untreated addiction. Preoccupation with achieving adequate pain relief can be appropriate behavior in a patient with poor pain control.

Abuse and addiction are separate and distinct from physical dependence and tolerance. Healthcare providers should be aware that addiction may not be accompanied by concurrent tolerance and symptoms of physical dependence in all addicts. In addition, abuse of opioids can occur in the absence of true addiction.

Methadone hydrochloride tablets, like other opioids, can be diverted for non-medical use into illicit channels of distribution. Careful record-keeping of prescribing information, including quantity, frequency, and renewal requests, as required by state and federal law, is strongly advised.

#UTHealth Houston

Proper assessment and selection of the patient, proper prescribing practices, periodic re-evaluation of therapy, and proper dispensing and storage are appropriate measures that help to limit abuse of opioid drugs.

Risks Specific to Abuse of Methadone Hydrochloride Tablets

Abuse of methadone hydrochloride tablets poses a risk of overdose and death. This risk is increased with concurrent abuse of methadone and alcohol or other substances. Methadone hydrochloride tablets are for oral use only and must not be injected. With intravenous abuse the inactive ingredients in methadone hydrochloride tablets can result in local tissue necrosis, infection, pulmonary granulomas, embolism and death, and increased risk of endocarditis and valvular heart injury. Parenteral drug abuse is commonly associated with transmission of infectious diseases such as hepatitis and HIV.

9.3 Dependence

Both tolerance and physical dependence can develop during chronic opioid therapy. Tolerance is the need for increasing doses of opioids to maintain a defined effect such as analgesia (in the absence of disease progression or other external factors). Tolerance may occur to both the desired and undesired effects of drugs, and may develop at different rates for different effects.

Physical dependence is a physiological state in which the body adapts to the drug after a period of regular exposure, resulting in withdrawal symptoms after abrupt discontinuation or a significant dosage reduction of a drug. Withdrawal also may be precipitated through the administration of drugs with opioid antagonist activity (e.g., naloxone, nalmefene), mixed agonist/antagonist analgesics (e.g., pentazocine, butorphanol, nalbuphine), or partial agonists (e.g., buprenorphine). Physical dependence may not occur to a clinically significant degree until after several days to weeks of continued opioid usage.

Do not abruptly discontinue methadone hydrochloride tablets in a patient physically dependent on opioids. Rapid tapering of methadone hydrochloride tablets in a patient physically dependent on opioids may lead to serious withdrawal symptoms, uncontrolled pain, and suicide. Rapid discontinuation has also been associated with attempts to find other sources of opioid analgesics, which may be confused with drug-seeking for abuse.

When discontinuing methadone hydrochloride tablets, gradually taper the dosage using a patient-specific plan that considers the following: the dose of methadone hydrochloride tablets the patient has been taking, the duration of treatment, and the physical and psychological attributes of the patient. To improve the likelihood of a successful taper and minimize withdrawal symptoms, it is important that the opioid tapering schedule is agreed upon by the patient. In patients taking opioids for a long duration at high doses, ensure that a multimodal approach to pain management, including mental health support (if needed), is in place prior to initiating an opioid analgesic taper [see Dosage and Administration (2.6), Warnings (5.15)].

Infants born to mothers physically dependent on opioids will also be physically dependent and may exhibit respiratory difficulties and withdrawal signs [see Use in Specific Populations (8.1)].

Neonatal opioid withdrawal syndrome (NOWS) is an expected and treatable outcome of prolonged use of opioids during pregnancy [see Warnings and Precautions (5.5)].

